## 7. DRUG INFORMATION

### 7.1. **$^{68}\text{Ga}$ PSMA-HBED-CC IND 135,727 ([name], sponsor)**

- 7.1.1. **Availability.** Drug is available from the P E T Drug Manufacturing Unit at the University of Iowa Hospitals & Clinics.
- 7.1.2. **Compatibility.** No known compatibility issues.
- 7.1.3. **Storage and stability.** Store drug in shielded container as per local institutional guidelines. Drug has a 3 hour stability. Expiration is provided on label.
- 7.1.4. **Toxicities.** No known toxicities.

## 8. DOSE MODIFICATIONS & DELAYS

Not applicable.

## 9. ADVERSE EVENTS: REPORTING REQUIREMENTS

This study will also be monitored by internal oversight specialists at the University of Iowa. The Data and Safety Monitoring Plan of the Holden Comprehensive Cancer Center provides standard operating procedures to monitor all clinical cancer trials at the UIHC. All investigator-initiated trials are automatically monitored by the Data and Safety Monitoring Committee (DSMC). A detailed data and safety monitoring plan for this study is on file with the DSMC. This study has been assigned as a risk level 4 as an IND phase 2b/3 study.

### 9.1. **Determination of Reporting Requirements**

The clinical research team is responsible for collecting and recording the research data. As these results are collected, all toxicities and adverse events will be identified and reported to the principal investigator (PI). The PI will determine final relationship of the event to the investigational products ( $^{68}\text{Ga}$  PSMA-HBED-CC):

- Grade 1 and 2 events do not require attributions assigned.
- Grade 3 and higher adverse events require attribution assigned to  $^{68}\text{Ga}$  PSMA-HBED-CC.
- All serious adverse events (SAEs) require attribution to  $^{68}\text{Ga}$  PSMA-HBED-CC.

Toxicity will be graded according to NCI's Common Toxicity Criteria (CTCAE v4). The principal investigator will have final responsibility for determining the attribution of toxicity as it is related to the investigational product.

### 9.2. **Institutional Review Board reporting requirements**

Adverse events that meet criteria of both *serious* and *attributed* (possible, probable, or definite) to the study agent. Thus:

- Serious adverse events *only*
- Attributable to  $^{68}\text{Ga}$  PSMA-HBED-CC

Report to the IRB via HawkIRB within 10 business days of event

**9.3. FDA reporting requirements [[name], sponsor]**

Adverse events that meet criteria of *serious*, *unexpected*, and *attributed* (possible, probable, or definite) to Ga PSMA-HBED-CC must be reported to the sponsor or the sponsor's appointed designee:

- Serious adverse events only [21 CFR 312.32]
- Attributable to Ga PSMA-HBED-CC with a causal relationship as described [21 CFR 312.32 (c)(1)(i)]
- Unexpected, as defined by the FDA: "...not listed in the investigator brochure or is not listed at the specificity or severity that has been observed; or, if an investigator or, if an investigator brochure is not required or available, is not consistent with the risk information described in the general investigational plan or elsewhere in the current application, as amended."

**9.4. Routine Adverse Event Reporting Requirements to DSMC**

For non-serious adverse events, documentation must begin at radiotracer injection and continue through 24 hours post injection.

Routine adverse events will be reported by submission of an adverse events log to the DSMC at the time of DSMC review.

**9.5. Serious Adverse Event Reporting to DSMC**

Serious adverse events occurring after Ga PSMA-HBED-CC injection will require a notification to the DSMC within 1 business day of learning of the event. The SAE capture window will be from the administration of Ga PSMA-HBED-CC through 24 hours after administration. Serious adverse events that occur after this window are reportable if they are deemed reasonably attributed to the investigational drug, Ga PSMA-HBED-CC .

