#### 3.2. Exclusion Criteria

- 3.2.1. Cannot receive furosemide.
- 3.2.2. Allergy to sulfa or sulfa-containing medications.
- 3.2.3. History of Stevens-Johnson syndrome
- 3.2.4. Known Paget's disease
- 3.2.5. Uncontrolled intercurrent illness including, but not limited to, ongoing or active infection, symptomatic congestive heart failure, unstable angina pectoris, cardiac arrhythmia, or psychiatric illness/social situations that would limit compliance with study requirements.

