#### 5.1. Imaging preparation

- 5.1.1. **Oral hydration.** Participants will be encouraged to maximize hydration the day before and day of  $^{68}\text{Ga}$  PSMA-HBED-CC imaging.
- 5.1.2. **Furosemide.** 20 mg furosemide (IV push) will be administered concurrently or immediately after radiotracer administration to minimize PET scatter artifacts from excreted radiotracer accumulation in the kidney and urinary

bladder.

- 5.1.3. **Contrast.** Imaging contrast will not be ordered as part of this study.
- 5.1.4. **Voiding.** Participants will be asked to void their bladder immediately prior to radiotracer injection and before imaging.

5.2. **Ga PSMA-HBED-CC administration**

- 5.2.1. **Dose.** 3-7 mCi (111 – 259 MBq). Target 5 mCi.
- 5.2.2. **Route of administration.** Intravenous.
- 5.2.3. **Frequency.** Once per PET scan.
- 5.2.4. **Uptake time.** 75 minutes ± 25 minutes. Target 75 minutes

5.3. **Prohibited Medications**

None.

5.4. **PET/CT Imaging Procedures**

- 5.4.1. **Scan coverage.** Scan coverage will extend from mid-thigh to the base of the skull, starting from the mid-thighs to prevent urinary bladder radiotracer accumulation at the start of PET imaging. Subject to void immediately prior to imaging.
- 5.4.2. **Bed position.** Scan time will be dependent on scanner capabilities. At a minimum, 3 minutes per bed position will be used.
- 5.4.3. **Discharge.** Subject must be monitored for adverse events for a minimum of 2 hours post-injection.
- 5.4.4. **Local Analysis.** A board-certified nuclear medicine physician on-site will interpret the images within 3 business days of the imaging study. These interpretations will not be used for final evaluation, however regional positivity results will be collected as study data.
- 5.4.5. **Internal Blinded Reads.** Imaging data will be interpreted by two different readers in a random order at separate reading sessions. Cross sectional imaging from the PET will be available for anatomic correlation. Final reads for each subject will be interpreted as positive or negative for the presence of pelvic nodal disease, and positive or negative for the presence of osseous metastatic disease and soft tissue metastases outside of the pelvis. All readers will have undergone Ga PSMA PET training.
- 5.4.6. **Results dissemination.** Results will be shared with the subject's urologist and will be included in the subject's medical record.

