## 6.4. **Follow-up**

6.4.1. **Pathology.** Results from pathology ordered per standard of care up to 12 months post Ga PSMA-HBED-CC PET/CT, will be obtained for study analysis.

6.4.2. **Follow-up imaging.** Conventional imaging ordered per standard of care up to 12 months post Ga PSMA-HBED-CC PET/CT, will be obtained for study analysis. If the 1st Ga-68 PSMA-HBED-CC PET/CT scan shows lesions outside the pelvic region AND if imaging is NOT obtained per standard of care the research study will obtain a CT (abdomen and pelvis w/ contrast if contrast not contraindicated). Readers will be unblinded to all results and will be specifically informed of the location of the Ga PSMA-HBED-CC PET positive lesions so follow-up measurements may be performed on the same lesions.

6.4.3. **Laboratory.** Results from laboratory reports related to prostate cancer monitoring (e.g. PSA levels) ordered per standard of care up to 12 months post Ga PSMA-HBED-CC PET/CT, will be obtained for study analysis.

6.4.4. **Second Ga PSMA-HBED-CC PET/CT (if medically indicated).** If the 1st Ga PSMA-HBED-CC PET/CT scan shows lymph nodes or visceral (soft tissue) lesions positive for prostate cancer disease, but surgery or biopsy results in negative pathology; the subject may be asked to return to complete a 2nd Ga-68 PSMA-HBED-CC PET/CT imaging visit.

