12.2.1.3. Bone lesions: Given the high rate of false negative biopsies for osseous metastases in subjects with prostate cancer, subjects with negative bone biopsies of  $^{68}\text{Ga}$ -PSMA-HBED-CC PET positive lesions will be further evaluated:

- If pathology demonstrates an alternative diagnoses that is known to be  $^{68}\text{Ga}$ -PSMA-HBED-CC positive (eg Renal Cell Carcinoma metastases, Paget's disease), then this will be considered negative for disease.
- If pathology is indeterminate, then follow-up imaging as described below will be performed as per clinical standards at the site.

12.2.1.4. Although not routinely performed during standard practice, immunohistochemical staining for PSMA of tumor specimens (primary and lymph node metastases) may be performed, although not required.

12.2.1.5. All regions not sampled for biopsy/histopathology will be designated as indeterminate for disease by pathology. Conventional imaging follow-up may be used in these cases to determine tissue status.

12.2.2. Follow-up Imaging will be used as a secondary assessment for prostate cancer in the event pathology information is not available:

All subjects will be tracked for follow-up conventional imaging between 3-12 months post  $^{68}\text{Ga}$ -PSMA-HBED-CC (dedicated CT, MRI and/or bone scan) as per site standard of care. If no follow-up imaging has been performed within the 9 months following the  $^{68}\text{Ga}$ -PSMA-HBED-CC scan, then the research study will pay for an additional follow-up CT scan to be performed in the 9-12

month window post-Ga-PSMA-HBED-CC scan. Follow up imaging will only be performed on subjects that have positive Ga-PSMA-HBED-CC findings because conventional imaging assessment for disease is primarily targeting suspicious lesions identified by Ga-PSMA-HBED-CC PET/CT. Interpretation of follow-up imaging will be performed by local read. Preferably, the follow-up conventional imaging should be the same modality/modalities as the initial staging work-up to allow for reproducible and accurate comparisons. Conventional imaging standards as described below will be used to determine tissue positive for prostate cancer disease. Conventional imaging will not be used to determine negative prostate cancer disease regions due to its inherently low negative predictive value.

Tissue positive for prostate cancer disease based on follow-up imaging:

12.2.2.1. Lymph nodes will be assessed by change in size.

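### The written attribution and onward-reporting rules name only the tracer, so serious harm judged due to the mandated furosemide or the research CT has no required IRB route and, outside the 24-hour window, no required DSMC route

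*Combined protocol and SAP*

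**What the plan says.** **Study interventions other than the tracer.** Section 5.1.2 states that "20 mg furosemide (IV push) will be administered concurrently or immediately after radiotracer administration". The study calendar (section 11) marks furosemide at the injection visit, and its note c says that any second scan is done in the same way as the first. The first exclusion in 3.2 is "Cannot receive furosemide"; sulfa allergy and "History of Stevens-Johnson syndrome" are also listed. If the first PSMA scan shows lesions outside the pelvis and standard care provides no imaging, 6.4.2 says that "the research study will obtain a CT (abdomen and pelvis w/ contrast if contrast not contraindicated"). Section 12.2.2 says "the research study will pay for an additional follow-up CT scan to be performed in the 9-12" month window after the PSMA scan.

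**Safety rules.** Section 9.1 has all events reported to the principal investigator, who judges their relation to the investigational products, named there as the tracer alone. It says "Grade 3 and higher adverse events require attribution assigned to" the tracer, and asks the same for every serious event. Section 9.2 sets the IRB criterion as "Adverse events that meet criteria of both *serious* and *attributed* (possible, probable, or definite) to the study agent", then restates the agent as the tracer. Section 9.3 applies a serious, unexpected and tracer-attributed test for the sponsor and FDA route. Section 9.5 captures serious events of any cause from tracer administration through 24 hours for the DSMC. After that, "Serious adverse events that occur after this window are reportable if they are deemed reasonably attributed to the investigational drug", which it names as the tracer.

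**The concern.** Furosemide is given because the protocol requires it, and the research CT is done because the study obtains it. Harm from either is harm from taking part. The protocol recognises that furosemide carries risk, since inability to receive it is an exclusion, while 7.1.4 lists no known toxicities for the tracer. Yet the tracer is the only cause to which the rules provide for attribution. A serious event that the investigator ascribes to furosemide or to the CT therefore fails the IRB test in 9.2 and, outside the 24-hour window, the DSMC test in 9.5. At stake is whether the two oversight bodies must be told of serious harm from everything the study does to subjects. Sample size, endpoints and diagnostic-accuracy analyses are not affected.

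**Working it through.** The only figure involved is the active follow-up period in 5.9.1, which reproduces: 10 half-lives × 67.71 min = 677.1 min; 677.1 / 60 = 11.3 h, rounded up to 1 calendar day. The stated basis is tracer decay alone. It gives no information about when a reaction to furosemide or contrast would appear.

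**Timing of the research CT.** Taking the earliest point in 12.2.2 and assuming 30.4 days per month, 9 × 30.4 × 24 = 6,566 h after injection, against a 24 h capture window. The CT falls outside the window unless a second tracer injection happens to precede it by less than a day. Attribution to a tracer with a 67.71-minute half-life is not realistic at that distance. Section 6.4.2 gives no date for its CT; I assume that it is the one timed in 12.2.2, although the two sections word the trigger differently.

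**Applying the rules as written to serious events:**

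| Serious event | Investigator (9.1) | IRB (9.2) | DSMC (9.5) |
|---|---|---|---|
| Starts within 24 h, judged due to furosemide and not to the tracer | told; tracer attribution recorded | not required | required (any cause) |
| Starts within 24 h, rated at least possible for the tracer | told; tracer attribution recorded | required | required |
| Starts after 24 h, judged due to furosemide and not to the tracer | told; tracer attribution recorded | not required | not required |
| Caused by the research CT, 9–12 months | told; tracer attribution recorded | not required | not required |

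Three points on reading the table:

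1. The opening sentence of 9.5 covers serious events after injection without a time limit. The next two sentences set the 24-hour window and the tracer-only rule beyond it, so I read it as limited.
2. Section 6.3.3 and calendar note g require a contact after 24 hours. A serious reaction on day 2 could therefore be found by the study and reach the investigator, with no written rule sending it further unless the tracer is implicated.
3. The calendar shows no adverse event query in long-term follow-up. The rule that the investigator is told would apply to a CT reaction, but no scheduled query is aimed at finding one.

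Section 9.3 is not counted as a gap. It is the IND route for the investigational drug, and a tracer-only test is appropriate there.

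**The case against.** The strongest reply is that the protocol is not the whole safety system. Section 9 refers to a detailed data and safety monitoring plan held by the DSMC, and 10.2 has monitors check serious-event reporting against institutional and federal requirements. Either may cover harm from study procedures. This stands as a limit on the claim: what is shown is a gap in the protocol text, not in oversight as a whole. It does not remove the point, because 9.2 and 9.5 state tracer-only conditions outright, and staff working from the protocol would follow them.

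Several stronger readings are tempting and should not be made:

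- *Nobody hears of a late furosemide reaction.* Section 9.1 sends all events to the investigator and requires attribution for every serious event, whatever its cause. What is missing is a required onward route.
- *The IRB never hears of an acute furosemide reaction.* The two drugs are given together and the threshold in 9.2 includes a possible relation. An investigator could reasonably rate an acute reaction as possible for the tracer, and it would then go to the IRB. The gap applies only to events judged not due to the tracer.
- *The sulfa and Stevens-Johnson exclusions show that the protocol foresaw furosemide reactions.* Section 3.2 gives no reasons. Only the exclusion that names furosemide supports the point directly. These exclusions may also lower the risk.
- *Sections 5.1.3 and 6.4.2 contradict each other on contrast.* Section 5.1.3 sits under preparation for the PSMA scan and may concern that scan only. Its wording refers to the whole study, so its scope needs stating, but a contradiction is not established.
- *The tracer's safety record will be distorted.* Events could be charged to the tracer for want of another category, but the documents give no basis for saying how often.

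**Conclusion.** The concern holds for the protocol as written. A serious event judged due to furosemide and not to the tracer has no required IRB route, and a required DSMC route only if it starts within 24 hours of tracer administration. A serious event from the research CT has no required route to either body. Exposure to furosemide is universal: all 30 planned subjects if all are imaged, with a second exposure for anyone rescanned. The documents do not allow an estimate of how many would have the research CT, or of how many serious events either intervention would cause; with 30 subjects the number may well be zero.

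The conclusion assumes that 9.5 is limited by its second and third sentences, that the study agent in 9.2 means the tracer (as its own restatement says), and that the CT in 6.4.2 follows the timing in 12.2.2. It could be softened by the monitoring plan on file or by institutional rules. This is a modest safety-reporting gap that is cheap to close.

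**What to change.** - In 9.1, 9.2 and 9.5, widen the object of attribution from the tracer alone to the tracer, the protocol-mandated furosemide, or a research-only procedure, including the research CT in 6.4.2. Record the attribution to each separately, so that the tracer's own record stays clean.
- Add a serious-event capture window after any research CT, with its length set by the sponsor and a matching adverse event query in the calendar.
- Leave 9.3 tracer-only.
- Check the monitoring plan on file. If it already covers these events, align 9.1, 9.2 and 9.5 with it and cite it there.
- State whether 5.1.3 concerns the PSMA scan only; if it does not, reconcile it with 6.4.2.

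The cost is a wording amendment to three sections, extra attribution fields on the adverse event log, one added query for subjects who have the research CT, and possibly a few more IRB or DSMC reports. Sample size, endpoints and analysis do not change.

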## **10. CLINICAL TRIAL MONITORING**

Clinical trial monitoring will be conducted to ensure that the rights and well-being of human subjects are protected, that the reported trial data are accurate, complete, and verifiable, and that the conduct of the trial is in compliance with the currently approved protocol and/or amendment, with good clinical practice (GCP), and with applicable regulatory requirement(s).

**10.1. University of Iowa's Human Subjects Office**

The University of Iowa's Human Subjects Office (HSO) provides five different monitoring visits (post-approval responsibilities review, post-approval monitoring and education visit, directed monitoring, department of defense sponsored research monitoring, student principal investigator review). The HSO also provides an IND educational visit combined with a post-approval responsibilities review.

- Monitoring is performed by the HSO from their roster of qualified individuals.
- Monitoring is on-site.
- An educational IND visit will be requested by the PI. This will be done after IRB approval. The IRB indicate if accrual can begin prior to this visit.

- For the educational IND visit, if subjects have been consented, all signed consent documents will be reviewed.
- For the educational IND visit, the principal investigator will be provided a copy of the report documenting the visit within 1 month.
- Monitoring plans are not study specific. The plans are maintained by the HSO and are available for public review on-line.

#### 10.2. **The Holden Comprehensive Cancer Center**

The Holden Comprehensive Cancer Center (HCCC) will provide monitoring for this investigator-initiated trial in compliance with their overarching monitoring plan on file with the National Cancer Institute (NCI) as well as with the individual clinical monitoring plan on file for this trial. Specifically:

- Monitoring is performed by the HCCC from their roster of qualified individuals.
- Eligibility review is ongoing, through remote review from OnCore, the clinical trials software
- Monitoring is on-site and begins with the accrual of the first subject and will be performed at least twice per year. Frequency is adjusted based on risk, reported SAEs, compliance, patient population, and accrual rate.
- A minimum of 25% of subjects will be monitored for the entire study.
- Items reviewed include: eligibility, consent document, compliance to protocol, SAE reporting per institutional and federal requirements, accuracy of data against primary source, and investigational drug documentation.
- The sponsor-investigator will be provided draft copies of the report within one month of the visit.
- Independent audits will be conducted by the HCCC to verify monitoring is being performed per the filed clinical monitoring plan. The audit procedures are documented in their Quality Assurance Management Plan on file with the NCI.

## 11. STUDY CALENDAR

	Screening	Baseline	V1 - PSMA-HBED-CC PET/CT b,c		Follow-up	
			Injection	Scan	Immediate	Long-term
Karnofsky PS a	X					
informed consent	X					
PSA		≤3 mo V1				X d
imaging pull		≤3mo V1				X d
pathology pull	X	≤3 mo V1				X d
 Ga PSMA-HBED-CC			5 mCi			
20 mg IV furosemide			X			
HR, BP, Temp			supine e	supine c		
voiding				X f		
Adverse event query g		X	X	X g		

a within 3 months of date eligibility is assessed.

b Scan will be clinically interpreted, and entered into the medical record.

c A 2nd Ga PSMA-HBED-CC PET/CT imaging visit may occur, if medically indicated. The 2nd scan will be obtained identical to 1st scan.

d data from follow-up imaging, laboratory PSA levels, and pathology as ordered for standard of care or study purposes will be analyzed and mined for outcomes

e HR, BP, temp performed with subject supine immediately before and after injection and post-imaging of the scan

f subject should void immediately prior to the scan.

g final adverse event assessment is done 1 to 3 days post-injection but no earlier than 24 hours post-injection

## 12. EFFICACY ASSESSMENTS

Determination of efficacy requires two primary assessments.

The first assessment is the clinical read of the  $^{68}\text{Ga}$ -PSMA-HBED-CC PET/CT scan. Trained readers will identify lesions positive for prostate cancer disease, and based on these results, will categorize specifically defined anatomical regions of the subject (Table 12.2) as positive for disease by  $^{68}\text{Ga}$ -PSMA-HBED-CC PET/CT. Criteria are described in Section 12.1 below.

The second assessment is the reference standard determination of disease positivity or negativity also performed on the same specifically defined anatomical regions (Table 12.2). The reference standard definitions are described below, and consist of a combination of pathological confirmation, conventional imaging follow-up evidence, and serial PSA measurements. Criteria are described in Section 12.2 below.

For purposes of endpoints, four major regions are identified for final analysis as defined in Table 12.1. Each region is divided into subregions as defined in Table 12.2. All primary data from  $^{68}\text{Ga}$ -PSMA-HBED-CC PET interpretations, pathology results, and conventional imaging results, will be collected per the subregions defined below. The final region assignments and results will be derived from the subregion data as applicable.

Region	Description
1	Prostate Bed
2	Pelvis outside of prostate bed including lymph nodes
3	Extrapelvic soft tissue, lymph nodes and organ metastases (non-bone)
4	Bone metastases

Table 12-1. Major Analysis Regions

Region 2: Pelvis outside of prostate bed	Region 3: Extrapelvic soft tissue	Region 4: Bone metastases
Right obturator	Lung	Spine
Left obturator	Liver	Ribs
Right external iliac	Pancreas	Pelvis
Left external iliac	Spleen	Extremities
Right internal iliac	Intestine	Skull
Left internal iliac	Mesentary	Sternum
Other pelvic regions	Brain	Clavicle
	Other soft tissue	Other bone
	Abdominal nodes	
	Thoracic nodes	
	Other nodes	

Table 12-2. Subregion Classification

